8.4.5.1 Hypertension

Treatment of hypertension and goal BP will be in accordance with international guidelines. AZD4635 dose reduction and discontinuation guidelines for the management of hypertension are shown in [Table 10](#). Details on daily management of BP are provided in [Section 8.2.4](#).

Patients taking antihypertensive medications will take and record BP readings twice daily while at home (recommended 1 hour post-dose) for at least the first 3 weeks after starting study drug. Twice-daily monitoring should be re-implemented after any AZD4635 hold/dosing delay for 2 weeks or until the patient is re-established on a stable anti-hypertensive regimen, whichever takes longer. Patient BP readings should be reviewed with the study team on a weekly basis for the first 3 weeks of study treatment to ensure that BP guidelines are being correctly followed.

Table 10 AZD4635 dose modifications and discontinuation criteria for management of hypertension

Event severity	Antihypertensive therapy	BP monitoring	AZD4635 dose modification
Systolic BP 150 to 159 mm Hg or diastolic BP 90 to 99 mm Hg; medical intervention indicated; recurrent or persistent (≥ 24 hrs); symptomatic increase by >20 mm Hg (diastolic) or to $>150/90$ mm Hg if previously within normal limits	Initiate/escalate antihypertensive medication as per local guidelines. BP goal and the choice of the antihypertensive drug will be individualized for each patient.	Increase frequency of monitoring until stabilized to BP $<150/90$ mmHg	None

Event severity	Antihypertensive therapy	BP monitoring	AZD4635 dose modification

Grade 3 (systolic BP \geq160 mm Hg or diastolic BP \geq100 mm Hg); medical intervention indicated; more than one drug or more intensive therapy than previously used indicated
	
Initiate or maximize BP therapy as per local guidelines.
 
Consider consult with a BP management specialist
	
Increase frequency of monitoring until stabilized to BP $<$150/90 mmHg
	
May continue AZD4635 with optimization of antihypertensive management unless persistent BP-related clinical symptoms.
 
Hold AZD4635 if BP is not decreased to grade 2 within 48 hours after optimum therapy is instituted.
 
If BP is reduced to baseline or Grade 1 within 14 days and considered stable, AZD4635 may be resumed at original dose.
 
Discontinue AZD4635 if BP does not resolve to Grade 1 within 14 days.
 
Discontinue AZD4635 if BP systolic \geq180 mmHg and/or diastolic \geq110 mmHg)
 
Recurrence of Grade 3: Discontinue study drug.

Grade 4 Life-threatening consequences (e.g., malignant hypertension, transient or permanent neurologic deficit, hypertensive crisis); urgent intervention indicated
	
Initiate treatment per local guidelines, including hospitalization, ICU management, and IV therapy as necessary
		
Discontinue AZD4635

8.4.5.2 Nausea and vomiting

If a patient has a known history of nausea and vomiting with prior therapy, it is strongly recommended that prophylactic anti-emetics be initiated at the start of treatment. They should continue as required thereafter, in accordance with local treatment practice guidelines. Additionally, AZD4635 capsules can be taken with a light meal/snack which may improve tolerability (i.e., 2 pieces of toast or a couple of biscuits).

As per international guidance on anti-emetic use in cancer subjects (ESMO, NCCN), generally a single agent anti-emetic should be considered (e.g., dopamine receptor antagonist, antihistamines or dexamethasone).

8.4.6 Duration of therapy

Patients may continue to receive AZD4635 and/or other combination therapeutic agent as long as they are continuing to show clinical benefit, as judged by the Investigator, and in the absence of discontinuation criteria.

8.5 Pharmacokinetics

Venous blood samples (2mL each) for determination of concentrations of AZD4635 and its metabolites in plasma will be taken in this study for all modules.

Please refer to the module-specific appendix for AZD4635 collection time points.

8.5.1 Determination of drug concentration

Samples for determination of drug concentration in plasma will be analyzed by analytical test sites on behalf of AstraZeneca, using an appropriate bioanalytical method. Full details of the analytical method used will be described in a separate bioanalytical report.

All samples still within the known stability of the analytes of interest at the time of receipt by the bioanalytical laboratory will be analyzed.

In addition, the PK samples may be subjected to further analyses in order to further investigate the presence and/or identity of drug metabolites. Any results from such analyses will be reported separately from the CSR, but known metabolites will be reported in the CSR.

Incurred sample reproducibility analysis, if any, will be performed alongside the bioanalysis of the test samples. The results from the evaluation will not be reported in the CSR but separately in a Bioanalytical Report.

8.5.2 Storage and destruction of pharmacokinetic samples

Pharmacokinetic (PK) samples will be disposed of after the bioanalytical report finalization or 6 months after issuance of the draft bioanalytical report (whichever is earlier), unless requested for future analyses.

Pharmacokinetic samples may be disposed of or anonymized by pooling. Additional analyses may be conducted on the anonymized, pooled PK samples to further evaluate and validate the analytical method. Any results from such analyses may be reported separately from the CSR.

8.6

CCI

CCI

8.7

CCI [Redacted]

8.7.1

CCI [Redacted]

CCI [Redacted]

8.7.2

CCI [Redacted]

CCI [Redacted]

8.8

CCI [Redacted]

CCI [Redacted]

8.8.1 CCI [Redacted]

8.8.1.1 CCI [Redacted]

CCI [Redacted]

8.8.2 CCI [Redacted]

CCI [Redacted]

8.8.3

CCI

CCI

8.8.4

CCI

CCI

8.8.5

CCI

CCI

8.9 Medical Resource Utilization and Health Economics

Medical resource utilization and health economics are not evaluated in this study.

9 STATISTICAL CONSIDERATIONS

A comprehensive statistical analysis plan will be developed and finalized before database lock and will describe the patient populations to be included in the analyses (performed by AstraZeneca and/or a third party), and procedures for accounting for missing, unused, and spurious data. This section is a summary of the planned statistical analyses of the primary and secondary endpoints. Any deviations from this plan will be reported in the clinical study report.

The primary aim of the study is to assess the efficacy, safety, and tolerability of multiple study drugs in patients with prostate cancer.

9.1 Statistical hypotheses

Not applicable

9.2 Sample size determination

The study is a Phase 2a signal searching study and consists of multiple single arm cohorts under a modular protocol. There are no plans to formally compare between the cohorts and this is not part of the study objectives. The aim is to identify treatment(s) to take forward into further trial(s). As such, there are no formal statistical hypothesis tests associated with the study objectives; statistical analysis of all study endpoints is descriptive.

The primary efficacy endpoint is PSA decline from baseline measure $\geq 50\%$ (PSA50) and overall response rate (ORR) per RECIST v1.1. The PSA endpoint will be used to define the sample size for patients with and without measurable disease at baseline.

In Module 1, 2, and 3 (if conducted) there will be approximately 30 PSA evaluable patients in each module, and approximately 20 patients will have RECIST measurable disease at baseline in each module.

In Module 1, 2, and 3 (if conducted) approximately 30 patients with and without measurable disease at baseline will be assessed for PSA50 in each module. CCI

In Module 1, 2, and 3 (if conducted), approximately 20 patients with measurable disease at baseline will be assessed for ORR in each module. CCI

If any of the required patients for PSA and/or ORR are not evaluable for PSA response or tumor response, respectively, they may be replaced at the sponsor's discretion.

9.3 Populations for analyses

For purposes of analysis, the following populations are defined:

Population	Description
Pharmacokinetics	Dosed patients with at least 1 reportable PK concentration
Tumor response	Dosed patients with a baseline tumor assessment, and measurable disease at baseline.
PSA response	Dosed patients with an abnormal baseline PSA data (≥ 1 ng/mL)
Evaluable for efficacy	Dosed patients with a baseline tumor assessment.
Safety analysis set	All patients who received at least 1 dose of study drug

Summaries of PK data for AZD4635 will consider the subset of the PK analysis set with evaluable PK data at that visit for which there are no important AEs or protocol deviations that may impact PK at that visit.

In the case of an important protocol deviation that affects the evaluability of the PK analysis, affected PK data collected will be excluded from the summaries, but will still be reported in the study result listings. Important deviations will be listed and summarized in the CSR.

9.4 Statistical analyses

All analyses will be reported per module.

9.4.1 Definition of endpoints

To meet the objectives for this study, data for the following endpoints will be collected:

- PSA response (Primary)
- Overall Response Rate (Primary)
- AZD4635 and metabolites PK concentrations (Secondary)
- Durvalumab and oleclumab PK concentrations (Secondary)
- Tumor response (Secondary)
 - DOR
- Overall survival (OS) (Secondary)
- Radiological progression-free survival (rPFS) (Secondary)
- CCI [REDACTED]
- CCI [REDACTED]
- Immunogenicity (ADA) (Secondary)
- Safety and Tolerability
 - AEs/SAEs

- Physical exam and vitals
- Clinical chemistry/hematology parameters
- CCI [REDACTED]
- CCI [REDACTED]

9.4.2 Demographic data

Characteristics of the patients, including medical history and disease characteristics at baseline, will be listed for each patient and summarized by module where appropriate.

9.4.3 Exposure

Exposure to IPs, i.e., total amount of study drug received, will be listed for all patients.

Reasons for discontinuation of IP will be listed including the study day of treatment discontinuation and will be summarized by dose level if appropriate.

Total exposure and total time on study (date of last dose minus date of first dose) will be summarized by the following: mean, standard deviation, minimum, maximum, median and number of observations. In addition, the number and percentage of patients with at least one dose interruption and at least one dose reduction will be presented separately for the initial period of evaluability (defined as 21 days) and for any time following this initial period of the study.

Relative Dose Intensity (RDI) will be calculated, and is defined as follows:

- $RDI = 100\% * d/D$, where d is the actual cumulative dose delivered up to the earlier of progression (or a censoring event) or the actual last day of dosing and D is the intended cumulative dose up to the earlier of progression (or a censoring event) or the actual last day of dosing plus the protocol-defined post-dose rest period.
-

9.4.4 Efficacy analyses

PSA response

PSA response is defined as the proportion of patients achieving a $\geq 50\%$ decline from baseline to the lowest post-baseline PSA results, confirmed by a second consecutive PSA assessment at least 3 weeks later. Ignore early rises (before 12 weeks) in determining PSA response.

- A patient will be regarded as having a single PSA visit response if their PSA level at any post-dose visit is reduced by 50% or more compared with baseline
- A patient will be regarded as having a confirmed PSA response if they have a reduction in PSA level of 50% or more compared with baseline that is confirmed at

the next assessment at least 3 weeks later (i.e., decrease relative to baseline of at least 50% documented on 2 consecutive occasions at least 3 weeks apart).

PSA progression

If there is a PSA decline from baseline, progression is defined as the date of the first PSA increase that is both $\geq 25\%$ and ≥ 2 ng/mL above the nadir and which is confirmed by a second value ≥ 3 weeks later, even if within 12 weeks.

If there is no PSA decline from baseline, progression is defined as a $\geq 25\%$ increase and ≥ 2 ng/mL increase from baseline beyond 12 weeks.

The proportion of patients achieving a PSA response and patients with a confirmed PSA response will be presented with 95% CI. The best PSA percentage change from baseline and the percent change from baseline in PSA levels at 12 weeks will be summarized and graphed. Waterfall plots (bar plots), and spider plots (individual line plots of percent change from baseline over time) will be produced.

Tumor response

Tumor response data will be summarized for dosed patients with measurable disease at baseline and separately for dosed patients that had measurable or non-measurable disease at baseline.

Tumor response data will be listed and summarized by dose, if appropriate, using the following response categories: CR, PR, SD, PD, and not evaluable (NE).

Best objective response and ORR will be summarized. Percentage change from baseline in tumor size will be determined for patients with measurable disease at baseline and is derived at each visit by the percentage change in the sum of the diameters of TLs.

Waterfall plots (bar plots), and spider plots (individual line plots of percent change from baseline over time) indicating the percentage change from baseline in sum of the diameters of TLs will be produced by dose level.

Duration of response (DoR) will be defined as the time from the date of first documented response (which is subsequently confirmed using RECIST v1.1) until date of documented progression or death in the absence of disease progression. The end of response should coincide with the date of progression or death from any cause used for the PFS endpoint. The time of the initial response will be defined as the latest of the dates contributing towards the first visit that was PR or CR that was subsequently confirmed.

If a patient does not progress following a response, then their duration of response will use the PFS censoring date as the date at which that subject is censored for DoR.

CCI

Radiological progression-free survival (rPFS)

Progression-free survival is defined as the time interval from the first dose of AZD4635 until the date of objective disease progression or death (by any cause in the absence of progression) regardless of whether the patient withdraws from treatment or receives another anti-cancer therapy prior to progression. Patients who have not progressed (defined as CR, PR or SD by RECIST v1.1 for soft tissue disease, or non-PD for bone disease, see [Appendix G](#)) at the time of analysis will be censored at the time of the last evaluable RECIST assessment or bone scan.

However, if the patient progresses or dies after 2 or more missed radiologic visits the patient will be censored at the time of the last evaluable RECIST v1.1 or bone scan assessment prior to the 2 missed visits. If a patient has an assessment for soft tissue disease (MRI/CT) but not for bone disease (bone scan), or vice versa, then this will count as a missed assessment. If the patient has no evaluable post-baseline RECIST v1.1 or bone scan assessment they will be censored at 1 day unless they die within 2 visits of baseline (in which case their date of death will be used).

Progression-free survival will be derived based on scan/assessment dates not the scheduled visit dates. If RECIST v1.1 assessments/bone scans contributing toward a particular visit are performed on different dates then the date of progression will be determined based on the earliest of the dates of the component that triggered the progression. With regard to censoring, a patient will be censored at the latest of the dates contributing to a particular overall visit assessment.

Overall survival

Overall survival is defined as the time from the first dose of AZD4635 until death due to any cause regardless of whether the patient withdraws from study therapy or receives another anti-cancer therapy. Any patient not known to have died at the time of analysis will be censored based on the last recorded date on which the subject was known to be alive.

Note: Survival calls will be made in the week following the date of data cut-off (DCO) for the analysis, and if subjects are confirmed to be alive or if the death date is after the DCO date these subjects will be censored at the date of DCO. See [Section 7](#) for methods that can be used to determine status of subjects who withdraw consent or are lost to follow-up.

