8.1 Efficacy assessments

All patients are expected to have both CT/MRI/PET and bone scans at each scheduled disease assessment. Evaluation of objective tumor response in this study will be done using RECIST v1.1 Criteria in evaluable soft tissue disease (see [Appendix G](#)). Tumors will be assessed at screening according to the module-specific SoA. Reassessment of tumors will be done by the same methods used to establish baseline tumor measurements.

PCWG3 PSA criteria ([Appendix I](#)) will also be used to evaluate response and progression. These criteria will be followed for determining the change in PSA levels. Prostate-specific antigen (PSA) levels in this study will be measured at screening, at the start of each new treatment cycle, at the end of study visit, at any other timepoints indicated in the SoA, and as clinically indicated.

Disease progression will be deemed to have occurred if 1 or more of the following criteria is met:

- Soft tissue disease progression as defined by RECIST v1.1
- Bone lesion progression by PCWG-3 ([Table 7](#))
- Death

Patients with PSA progression are permitted and encouraged to continue treatment until symptomatic or radiographic progression. Sites should monitor PSA by cycle but plan to continue through early rises for a minimum of 12 weeks unless there is other evidence of progression.

All CT/bone scans and all imaging assessments performed for RECIST 1.1 tumour assessment will be reviewed at site. Duplicates must be available at the site in readiness to be sent for retrospective independent central RECIST 1.1 review, if deemed appropriate. More information on this procedure is available in the Image Acquisition Guideline for this study.

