2 or more new metastatic bone lesions are observed compared to the 6-week assessment. The confirmatory scan, performed at least 6 weeks later and preferably at the next scheduled visit for a bone scan, must show the persistence of or an increase in the number of metastatic bone lesions compared to the prior scan for progression to be documented.

The date of progression is the date of the scan that first documents the second lesion.

Evaluation of bone progression status

Table 15 provides the definitions for the visit bone progression status for bone lesions.

Table 15 Bone progression status

Non Progressive Disease (Non-PD)	No evidence of progression, or appearance of one new bone lesion, or non-fulfillment of the progression criteria including new lesions without confirmation of progression.
Progressive Disease (PD)	Bone lesions fulfilling the requirements for at least 2 new lesions and confirmation of progression.
Not Evaluable (NE)	Only relevant if a follow-up bone scan is not performed

OVERALL RADIOLOGICAL VISIT ASSESSMENT

Table 16 provides the definitions how the visit responses for soft tissue (according to RECIST1.1 criteria) and bone progression status (according to PCWG3 criteria) are combined to give an overall radiological objective visit response.

Table 16 Overall radiological visit response

Overall visit soft tissue response (RECIST 1.1)	Bone progression status (PCWG3)	Bone lesions at visit Present/Absent	Overall radiological visit response
CR	Non-PD	Absent	CR
CR	Non-PD	Present	PR
CR	NE	-	PR
PR	Non-PD or NE	Any	PR
SD	Non-PD or NE	Any	SD
NED	Non-PD or NE	Any	Non-PD
NE	Non-PD or NE	Any	NE

Table 16 Overall radiological visit response

Overall visit soft tissue response (RECIST 1.1)	Bone progression status (PCWG3)	Bone lesions at visit Present/Absent	Overall radiological visit response
PD	Any	Any	PD
Any	PD	Any	PD

CR = complete response, PR = partial response, SD = stable disease, PD = progressive disease, NE = not evaluable, NED = No Evidence of Disease (only relevant when there is no TL and NTL from baseline).

CONFIRMATION OF RESPONSE

In the D8731C00001 study, imaging for confirmation of response (CR or PR) should be performed at the next scheduled RECIST and PCWG3 assessment, i.e., 8 weeks (and must not be less than 4 weeks later) following the date the criteria for response were first met.

Table 17 Best overall response when confirmation of CR and PR required.

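### A visit with CT/MRI but no bone scan counts as missed for rPFS yet as evaluable for response, so documented progressions can be censored and a confirmed responder's DoR can end before it begins

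*Protocol*

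**What the plan says.** Section 8.1 sets the expectation: "All patients are expected to have both CT/MRI/PET and bone scans at each scheduled disease assessment". The rules below therefore differ only when a scan is skipped.

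- **rPFS, Section 9.4.4.** A visit with CT/MRI but "not for bone disease (bone scan), or vice versa, then this will count as a missed assessment". The consequence is that "if the patient progresses or dies after 2 or more missed radiologic visits the patient will be censored" at the last evaluable RECIST or bone scan assessment before the two missed visits. A patient with no evaluable post-baseline assessment of either kind is censored at 1 day, unless death occurs within two visits of baseline.
- **rPFS censoring of non-progressors, same section.** They "will be censored at the time of the last evaluable RECIST assessment or bone scan", so either component is enough here.
- **Visit response, Appendix G.** Table 15 defines bone status NE as "Only relevant if a follow-up bone scan is not performed". Table 16 then combines soft tissue with bone NE as follows: CR becomes PR, PR stays PR, SD stays SD, and PD is PD whatever the bone status.
- **DoR, Section 9.4.4.** "The end of response should coincide with the date of progression or death from any cause used for the PFS endpoint". For a responder who does not progress, "duration of response will use the PFS censoring date as the date at which that subject is censored for DoR".

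**The concern.** The same visit can establish or confirm a response and also be treated as not having taken place for rPFS. Section 9.4.4 is also at odds with itself: it accepts either component as evaluable when it sets a censoring date, but calls a visit with one component missed.

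Two things are at stake. First, a progression seen on CT, or a death, can be removed from the rPFS analysis although it was observed. Which patients lose their event depends on how long they stayed progression-free, because two earlier visits are needed, so the censoring is informative. Second, DoR inherits the PFS dates and can become impossible. The 6-month rPFS proportion and DoR are both named secondary endpoints in Section 3.

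**Working it through.** The protocol states no figure for rPFS or DoR, so there is none to reproduce.

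**1. The two rules side by side**

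| Visit | Tables 15 and 16 | Section 9.4.4 |
|---|---|---|
| CT PR, no bone scan | PR | missed |
| CT SD, no bone scan | SD | missed |
| CT PD, no bone scan | PD | missed; whether the PD itself counts is not said |
| Bone scan non-PD, soft tissue NE | NE | missed |

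The clash is mainly on the CT-only side. With a bone scan alone and no bone PD, the two rules agree that the visit is not evaluable.

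**2. When an event is lost**

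Scans fall at Week 6 and then every 8 weeks: 14, 22, 30, 38 (Section 8.1.1). Two missed visits must come first, so PD at Week 6 or 14 is never lost. PD at a scheduled visit within 26 weeks is lost only if Weeks 6 and 14 were both single-scan and PD is seen at Week 22.

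**3. DoR example (needs no assumed skip rate)**

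Take both scans at Week 6, CT-only PR at Week 14, CT-only PR at Week 22 (which confirms the response), and PD at Week 30. Under Section 9.4.4, Weeks 14 and 22 are missed, so rPFS is censored at Week 6. The response began at Week 14. If DoR takes the PFS censoring date, it is 6 − 14 = −8 weeks. If the DoR censoring sentence is held not to apply because he did progress, DoR has no end date, since PFS has no event for him.

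**4. Size for 6-month rPFS**

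Assumptions:
- exponential rPFS with median 14.9 weeks (the earlier combination cohort, Section 2.3)
- all progression visible on CT and counted at the visit where it is seen
- a share q of patients who never have a follow-up bone scan (q is not in the documents)
- every patient followed to progression

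With S(t) = exp(−ln 2 · t/14.9): S(6) = 0.7564, S(14) = 0.5214, S(22) = 0.3594, S(30) = 0.2477, S(38) = 0.1707. Progressions first seen at Weeks 6, 14, 22, 30 and 38 are 0.2436, 0.2351, 0.1620, 0.1117 and 0.0770 of patients.

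*Table 16 reading.* The Kaplan-Meier estimate at 26 weeks is S(22) = 35.9%.

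*Day-1 reading, q = 0.2.* CT-only patients with PD at Week 22 or later leave at Day 1: 0.2 × 0.5214 = 0.104 of patients.
- Week 6: 1 − 0.2436/0.8957 = 0.7281
- Week 14: 1 − 0.2351/0.6522 = 0.6396
- Week 22: 1 − 0.1296/0.4171 = 0.6892
- Product: 32.1%. The same steps give 34.1% at q = 0.1 and 29.8% at q = 0.3.

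*Only the two visits just before PD, q = 0.2.* PD at Week 22 goes back to Day 1, PD at Week 30 to Week 6, and PD at Week 38 to Week 14.
- Week 6: 1 − 0.2436/0.9676 = 0.7483
- Week 14: 1 − 0.2351/0.7017 = 0.6650
- Week 22: 1 − 0.1296/0.4512 = 0.7128
- Product: 35.5%. At q = 0.1 and q = 0.3 it is 35.7% and 35.3%.

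*With a data cut-off.* Assume 18-month accrual and a cut-off 26 weeks after the last start. Simulation at q = 0.2 gives 36.1% under Table 16. Under the Day-1 reading it gives 33.8%, or 32.4% if non-progressors are also held to their last complete visit, with 9.4% of progressions discarded. Under the two-visits-before reading it gives 35.8%.

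*Random skipping.* If 20% of single visits lack a bone scan at random, the estimate moves from 36.0% to 35.8% or 35.7%. If the two missed visits need not be consecutive, a simulation stopped at Week 30 moves from 35.9% to 35.4% at 20% and from 36.0% to 33.9% at 50%.

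*Direction.* At a median of 29.3 weeks (the upper confidence limit in Section 2.3), with q = 0.3 and follow-up stopped at Week 30, 59.8% becomes 60.7%.

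**The case against.** Requiring both scans is a defensible choice. rPFS is a composite of soft tissue and bone, and a CT alone cannot show that a patient is free of PCWG3 bone progression. Table 16 assigns a visit response, whereas Section 9.4.4 asks whether a visit is complete enough to support progression-free status. These are different questions. Section 8.1 expects both scans, so two skipped bone scans in one patient is a repeated deviation. The endpoints are secondary and descriptive. With about 30 patients, the 95% half-width near 36% is 1.96 × √(0.36 × 0.64/30) ≈ 17 points. Section 9 leaves missing-data procedures to the SAP, which may settle the matter.

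Most of this stands, and it limits the size of the point. It does not remove the conflict, because the protocol itself fixes both rules. Doubt about unseen bone progression is a reason not to credit a CT-only visit as progression-free. It is no reason to set aside a progression that was seen, and it does not explain a negative DoR.

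Two stronger readings are tempting. A reader might infer that the rule routinely deletes progressions and distorts 6-month rPFS. The documents do not support that: one CT-only visit deletes nothing, no skip rate is given, and under one reading the direction can reverse. A reader might also infer that every CT-only patient who progresses late is censored at Day 1. Section 9.4.4 reserves that date for patients with no evaluable post-baseline RECIST or bone scan assessment, and a CT-only patient has evaluable RECIST assessments. Day 1 is one reading of unclear text.

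**Conclusion.** The inconsistency is real and lies in the stated text: Section 9.4.4 against Tables 15 and 16, and Section 9.4.4 against its own censoring sentence. Followed literally, it can discard an observed progression or death after two single-scan visits and give a confirmed responder an impossible DoR. That second result rests on the rules alone.

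The effect on 6-month rPFS is conditional. It is under 1 point if 20% of visits lack the bone scan at random, or if only the two visits just before PD are used. It is about 2 to 4 points downward if 20% of patients never have follow-up bone scans and are censored at Day 1. These sizes assume exponential rPFS with a 14.9-week median, CT-visible progression and an invented skip rate. All are small beside the sampling error. The text should be corrected for coherence and for DoR; a material bias in rPFS has not been shown.

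**What to change.** Reconcile Section 9.4.4 with Tables 15 and 16:

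- Use one visit status for response, rPFS and DoR, with an absent component entered as NE and Table 16 deciding the visit.
- State that progression documented on either component (with whatever confirmation Table 7 requires), or death, is an event unless the two consecutive visits immediately before it had no evaluable imaging.
- State the censoring date that applies when that exception is met, including when Day 1 is used.
- Report the stricter both-scans rule as a sensitivity analysis, and tabulate how many visits lacked a bone scan and how many events the stricter rule removes.

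The cost is a wording change in the protocol and SAP and one extra table; no new data are needed. The downside is that crediting CT-only visits may miss bone progression or date it late in patients who skip bone scans. The sensitivity analysis is there to show how much that matters.
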